## **6.7 BASELINE, TIME WINDOWS AND CALCULATED VISITS**

As a general rule, the last assessment / measurement observed prior to start of study medication following ICF will be assigned to baseline. Note that for some study procedures

(e.g. body weight, vital signs) this may be the value measured on the same day trial medication was started

Visit windowing will be performed as described in [Table 6.7:1](#), in order to assign data to the relevant study visit based on the actual day of the assessment. Data will be analysed using the re-calculated visits in the statistical tables. However, in the listings, all visits performed will be displayed (even if outside time-window), along with the re-calculated visit.

Table 6.7:1 Analysis Visit Windows

Analysis Visits	Target Day 	Analysis visit window	Group 1	Group 2
Baseline	1	<=1	<=1	<=1
FU1 3 Months	92	52-132	52-132	52-132
FU2 6 Months	183	143-213		143-213
FU3 9 Months	275	235-315		235-315
FU4 12 Months	366	326-406		326-406

 The baseline visit (day 1): as documented in the eCRF (after the ICF has been signed). Any assessment following this date is subject to analysis visits window.

Group 1: Eligibility criteria, Co-morbidities, Baseline information (assessment), IPF risk factors, information on IPF, Functional assessment, Questionnaires

Group 2: Symptoms, LTOT,

AEs, survival status, concomitant medication treatment with Nintedanib are excluded from analysis visit mapping window and the investigator may enter data as needed.

Post baseline: Any assessment after the baseline visit and during the follow up visits.

If after windowing of visits at baseline, two or more values fall within the same baseline interval, then the last value will be taken into account. If after windowing of post-baseline visits, two visits fall in the same interval, then the measurement closest to the planned visit will be taken into account. In case two measurements are equidistant from the planned visit, then the last one will be picked.

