### **Inclusion criteria**

- Patients  $\geq$ 40 years of age.
- Patients that have signed Informed Consent Form.
- Treatment naive patients with an initial IPF diagnosis no more than 3 months prior to enrolment according to 2011 ATS/ERS/JRS/ALAT guidelines who are initiating treatment with nintedanib (as monotherapy for IPF), the latest on the enrollment day or have initiated treatment with nintedanib (as monotherapy for IPF) within the past 7 days prior to enrolment.
- Patients for whom the decision to prescribe therapy with nintedanib according to the locally approved product's Summary of Product Characteristics (SmPC) has already been taken prior to their enrolment in the study and is clearly separated from the physician's decision to include the patient in the current study.
- Patients that are able to read, understand and complete the study specific questionnaires.

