## **6. GENERAL ANALYSIS DEFINITIONS**

### **6.1 TREATMENT(S)**

Patients enrolled in the current trial are recently diagnosed IPF patients and they have already initiated treatment with Nintedanib according to their physician's clinical decision.

No treatment intervention is relevant and therefore no special treatment assignment is under consideration.

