### **6.2 IMPORTANT PROTOCOL DEVIATIONS**

Table 6.2:1 Important protocol deviations

Category/ Code	Description	Requirements	Excluded from
A	Entrance criteria not met		
A1.1	Inclusion criteria not met as specified in the protocol:	
The following inclusion criteria not met
 
 
• Patients <math>\geq 40</math> years of age.
 
• Treatment naïve patients with initial IPF diagnosis no more than 3 months prior to enrolment according to 2011 ATS/ERS/JRS/ALAT guidelines who are initiating treatment with Nintedanib (as monotherapy for IPF) or have initiated treatment with Nintedanib (as monotherapy for IPF) within the past 7 days prior to the enrolment.*
 
• Patients for whom the decision to prescribe therapy with Nintedanib according to the locally approved product's SmPC has already been taken prior to the study enrolment and is clearly separated from the physician's decision to include patient in the current study. *
 
• Patients that are able to read, understand and complete the study specific questionnaires. *
 
	PPS
A2	Exclusion criteria met		PPS
B	Informed consent		
B1	Informed consent not available/not done	Informed consent date missing	TS, PPS
B2	Informed consent too late	Informed consent date <actual consent date> was after Visit 2 date <Visit 2 date>	
D	Concomitant medication		
D2	Prohibited medication use	Pirfenidone taken.*	PPS
D3	Mandatory medication not taken	Nintedanib treatment was not taken or interrupted	PPS

Category/ Code	Description	Requirements	Excluded from
		for 28 days period*	
E	Certain Violations of procedures used to measure primary data		
E1	Protocol amendment / incorrect CRF, implemented after the approvals and/or PI signature	Incorrected (old) version of SGRQ questionnaire is completed after the IRB approvals*	PPS
F	Certain Violations of time schedule to measure primary data		
F1	No follow-up visits performed	Only baseline visit is recorded	PPS

Note: (\*) not programming activity checks. These IPV definitions in the TSAP should be made available to the Local Clinical Monitors (CMLs)/Clinical Research Associates (CRAs) to view so they know which IPVs are programmed and hence do not need to be identified at a site level on the manual PV log.”

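### Does the opening baseline rule in SAP 6.7 leave patients already on nintedanib at consent without a baseline?

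*SAP*

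**What the plan says.** **The opening rule.** SAP 6.7 begins, in terms hedged as applying in general, that "the last assessment / measurement observed prior to start of study medication following ICF will be assigned to baseline". It adds that for some procedures "this may be the value measured on the same day trial medication was started"; its examples are body weight and vital signs, not questionnaires.

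**The population.** SAP 6.1 says of the enrolled patients that "they have already initiated treatment with Nintedanib". Table 6.2:1 of the SAP (code A1.1) covers patients who are starting the drug and also those who "have initiated treatment with Nintedanib (as monotherapy for IPF) within the past 7 days prior to the enrolment". Protocol 9.2.2 has the same two routes.

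**The visit rule in the same section.** SAP 6.7 goes on: "Data will be analysed using the re-calculated visits in the statistical tables". In Table 6.7:1 the baseline window is day 1 or earlier, for both groups of variables. Its footnote defines the anchor: "The baseline visit (day 1): as documented in the eCRF (after the ICF has been signed". Treatment start is not mentioned. Group 1 includes "IPF risk factors, information on IPF, Functional assessment, Questionnaires". If several values fall in the baseline interval, the last is taken.

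**Elsewhere.** SAP 7.4.1 defines the SGRQ baseline as the score after consent and refers to Table 6.7:1. Protocol 9.7.1 puts baseline at enrolment, for the primary outcome and again under the secondary outcomes.

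**The concern.** Read in the natural way, the opening rule asks for a value that comes after consent and before the first dose. A patient who began nintedanib some days before consenting cannot have one. SAP 6.1 suggests that such patients are common, and no visible sentence says that Table 6.7:1 takes precedence.

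Change in SGRQ is the primary endpoint, and the repeated-measures models use baseline score by visit as a term. SAP 6.6 rules out imputation. A mixed model that assumes data missing at random copes with missing outcomes, but it drops a patient whose baseline covariate is missing. If the opening rule were programmed literally, already-treated patients would vanish from the change summaries and from the models for SGRQ, mMRC, Cough-VAS and GAD-7.

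The model covariates raise a similar question. Protocol 9.3.3 records FVC and DLCO only where the test has already been done, so values may predate consent, and GAP stage uses lung function as well. The opening rule would reject such values.

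**Working it through.** There is no stated figure to reproduce, so the check is one of logic.

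**1. Can the opening rule be met?** Inputs: nintedanib starts on the enrolment day at the latest, or up to 7 days before it (protocol 9.2.2). Assumption: consent and the baseline visit fall on the enrolment day, counted as day 1. With start *s* days relative to enrolment, the first dose falls on day 1 + *s*. The rule needs an assessment day *a* with 1 ≤ *a* < 1 + *s*, or *a* = 1 + *s* under the same-day allowance.

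| Start relative to enrolment (*s*) | First-dose day (1 + *s*) | Opening rule | Table 6.7:1 (day ≤ 1) |
|---|---|---|---|
| −7 to −1 (7 start days) | −6 to 0 | no value possible | day-1 value |
| 0 (1 start day) | 1 | same-day value only | day-1 value |

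The opening rule fails on 7 of the 8 permitted start days. The table fails on none.

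**2. Which rule produces the results?**

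- *SGRQ.* SAP 7.4.1 names Table 6.7:1 and sets no treatment-start condition, so the primary endpoint is settled.
- *Cough-VAS and GAD-7.* Protocol 9.7.1 gives them the same analysis as the primary outcome, with baseline at enrolment. The table's Group 1 also covers questionnaires.
- *mMRC.* SAP 7.5.2.1 does not cite the table, but protocol 9.3.3 lists mMRC among the questionnaires, so Group 1 applies.
- *FVC and DLCO.* Functional assessment is named in Group 1. A window of day 1 or earlier accepts values from before consent, and the last value in it is used. GAP stage can draw on the same lung-function values.

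**3. Is there a competing value?** Protocol Table 2 schedules one baseline visit with one set of SGRQ, mMRC, Cough-VAS and GAD-7. The two rules therefore do not pick different scheduled scores. One picks the only score there is, and the other picks nothing.

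**4. Size.** Let *f* be the share of patients with a first dose before the day of consent. No document gives *f*, so it is assumed to lie anywhere from 0 to 1.

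- Opening rule taken literally: *f* × 240, that is 0 × 240 = 0 up to 1 × 240 = 240 patients without a questionnaire baseline.
- Table 6.7:1: 0 patients, whatever *f* is.

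The first range only restates that *f* is unknown. It is not an estimate of loss.

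**The case for a change.** The best case for a change is that a SAP should be executable without inference. A programmer should not have to work out that the first sentence of a section is inoperative, least of all where it fixes the reference point of the primary endpoint. Losing most patients would be caught at a dry run; losing some might be taken for ordinary missing data. The repair would cost about two sentences.

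Part of this stands. The opening sentence does not fit the enrolled population, it disagrees with the table below it, and the visible text states no order of precedence.

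The rest is weaker. To do harm, a programmer would have to set aside the instruction to analyse on re-calculated visits, the table and its footnote, SAP 7.4.1 and protocol 9.7.1, and then blank the only baseline scores collected. The natural reading is also not the only one. The reference to consent can attach to the start of medication, meaning the first dose taken after consent; prior nintedanib would then not make the rule impossible, and lung function measured before consent would qualify. The covariate point is answered by the table's window. SAP 7.1 also refers to a Section 5.4.1 that is not visible, so it cannot be said that nothing more is specified there.

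**Conclusion.** The inconsistency is real but clerical. Read as a whole, the plan fixes baseline at the enrolment visit after consent for every questionnaire, and at the last value up to day 1 for lung function. On that reading 0 of 240 patients lose a baseline through this rule, and no estimate, confidence interval or sample-size figure changes. New wording would mostly restate Table 6.7:1 and protocol 9.7.1. For some patients baseline follows up to 7 days of drug, but that comes from the inclusion criteria and is the same whichever sentence of SAP 6.7 is kept.

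This rests on three assumptions: that analysts follow the table to which SAP 6.7 and 7.4.1 point; that consent and the baseline visit fall on the enrolment day; and that redacted SAP sections do not say otherwise. It is at most an editorial note for a SAP revision made for other reasons.

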#### **9.2.3      Study visits**

The study is scheduled to run for 4 years in total, i.e. 3 years of recruitment and 1 year of follow-up. During the follow up period, data will be collected on 4 standard clinical visits which usually are scheduled around: 3-months ( $\pm$  1 month), 6-months ( $\pm$  1 month), 9-months ( $\pm$  1 month), 12-months ( $\pm$  1 month) until the end of participation in the study. Patients that permanently discontinue nintedanib treatment for any reason (e.g. due to AE, consent withdrawal, lost to Follow-up) prior to the follow up period completion, will no longer be followed-up for the study and the visit that nintedanib discontinuation is recorded will be considered as their end of study visit.

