### **9.3.3 Covariates**

Due to the non - interventional nature and design of this study, it does not require strict timeline visit schedule. Patients will receive treatment with nintedanib according to standard clinical practice with regards to approximate visit frequencies described above, type of performed assessments and according to local prescription requirements.

Following identification of a potential patient, the investigator will follow the below listed procedures:

1. Review of individual patient's medical history, to confirm that the inclusion/exclusion criteria are met.
2. Explanation of the study objectives to the patient and receipt of signed and dated informed consent, after providing the patient with sufficient time to read carefully and understand the information sheet.
3. Data collection from the medical records of eligible for enrollment patients, as required by eCRF, and eCRF completion.

Please refer to [Section 11.2](#) for details regarding Adverse Event and Serious Adverse Event Collection and Reporting.

A tabulated schedule of assessments that provide information regarding the recommended timeline of data collection and represents the standard clinical care of IPF treated patients is listed below in [Table 1](#). The exact definitions of the variables are the following:

- Basic (Socio-) demographic data. Age (date of birth), gender (sex), race
- Anthropometric characteristics. Height and weight of the patients will be recorded

Proprietary confidential information © 2021 Boehringer Ingelheim International GmbH or one or more of its affiliated companies

- Physical and vital signs examination. Blood pressure (sitting systolic and diastolic arterial pressure), and heart rate will be recorded
- IPF risk factors. These include smoking habit (past or current smoker, non-smoker or unknown) and number of pack-years, environmental and occupational exposure; alcohol and substance abuse, exposure to drugs associated with pulmonary fibrosis, exposure to viral infection possibly related to IPF, gastro-esophageal reflux, genetic factors (family history), or others.
- Co-morbidities and concomitant treatments (medication category/class).
- Date and method of IPF diagnosis. Dates and results of High Resolution Chest CT (HRCT), surgical lung biopsy and bronchoalveolar lavage will be recorded if already performed
- IPF symptoms. Presence of dyspnea, cough, fatigue, dizziness, chest pain and anxiety as reported by the patient will be recorded.

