6-minute walk distance			
Treatment with Nintedanib (start date, stop date, restart date in case of temporary discontinuation and daily dose)	x	x	x
Long-Term-Oxygen-Therapy (liquid and/or concentrate)	x	x	x
Questionnaires			
SGRQ	x	x	x
mMRC	x	x	x

Cough - VAS	X	X	X
GAD-7	X	X	X
SMAQ		X	X
Survival status		X	X
Reason for treatment discontinuation			X

For abbreviations, please refer to glossary.

\*3-months ( $\pm$  1 month), 6-months ( $\pm$  1 month), 9-months ( $\pm$  1 month),

\*\* Final visit is designated as either the 12 months ( $\pm$  1 month) follow up visit for all patients that remain on study until that time-point or the visit performed at the time of a patient's discontinuation or withdrawal from the study.

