### 7.4 PRIMARY ENDPOINT(S)

#### 7.4.1 Primary analysis of the primary endpoint(s)

The SGRQ Total score and the corresponding sub domains will be calculated; it summarizes the impact of the disease on the overall health status. Scores are expressed as a percentage of

overall impairment where 100 represents worst possible health status and 0 indicates best possible health status.

The primary endpoint of SGRQ Total score and the corresponding sub domains will be summarized descriptively as continuous variables at each study visit in the TS population.

The SGRQ scores to be displayed in the above mentioned summaries will be the observed values at each visit and the absolute change from baseline at each visit.

Calculation of SGRQ score for each patient is performed on patient level based on the questionnaire manual.

Change from baseline is defined as post baseline – baseline value, assuming that both time points are non missing.

Baseline value: SGRQ following to ICF signature, see [Table 6.7:1](#).

Post baseline value: Any SGRQ score after the baseline visit.

For the statistical inference regarding the SGRQ Total score and the corresponding sub domains, mixed models for repeated measurements model (MMRM) assuming random missingness will be fit. The dependent variable will be the SGRQ (Total score or the corresponding subdomains) at each visit. Visit, GAPBSL stage, FVCBSL (cut off  $\leq 70\%$ ), DLCOBSL (cut off  $< 40\%$ ) and number of comorbidities (as dictated by the medical history page) will be entered as fixed factors, baseline score by visit as interaction term.

Patients will be fitted at random and an unstructured correlation matrix will be used, allowing adjustment for correlations between study visits within the study patients. The Kenward-Roger degrees of freedom approximation will be used in the model (ddfm=kr). In case of no convergence, the following steps will be considered:

- The value used in the model as tolerance in checking singularity should be changed to 10-10 (the default value is 10-12).
- Increase the number of convergence iterations to 200 (default is 100 iterations).
- Apply scoring algorithm. Request to use the Fisher scoring algorithm up to the 4th iteration. The default is 1.

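### SAP Table 6.7:1 ends the 6-month window ten days early and leaves gaps between visits, so some observed SGRQ records have no place in the primary tables or model

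*SAP*

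**What the plan says.** SAP section 6.7 re-labels visits by study day and then uses those labels for analysis: "Data will be analysed using the re-calculated visits in the statistical tables". The footnote to Table 6.7:1 makes the rule general after baseline: "Any assessment following this date is subject to analysis visits window". Only adverse events, survival status, concomitant medication and nintedanib treatment are exempt. The general window column gives FU1 52-132 (target 92), FU2 143-213 (target 183), FU3 235-315 (target 275) and FU4 326-406 (target 366).

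For visits outside a window, the section commits only to the listings, where "all visits performed will be displayed (even if outside time-window), along with the re-calculated visit". Its rule for duplicates applies when "two visits fall in the same interval, then the measurement closest to the planned visit will be taken into account".

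In SAP section 7.4.1 the primary model is by visit: "The dependent variable will be the SGRQ (Total score or the corresponding subdomains) at each visit", with visit as a fixed factor. The same section counts every SGRQ score obtained after baseline as post-baseline.

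Protocol section 9.2.3 describes follow-up loosely: "data will be collected on 4 standard clinical visits which usually are scheduled around" 3, 6, 9 and 12 months, each ±1 month. Section 9.3.3 says of the study that "it does not require strict timeline visit schedule". The footnote to Protocol Table 1 defines the final visit as the 12-month visit "or the visit performed at the time of a patient's discontinuation or withdrawal from the study". SGRQ is among the questionnaires for that final visit.

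**The concern.** The primary endpoint is SGRQ change from baseline at 3, 6, 9 and 12 months. Under the SAP, a record enters the by-visit summaries and the MMRM only if it carries an analysis-visit label, and the windows do not give a label to every day. Two things look wrong.

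First, FU2 alone is asymmetric, and its short side is tight enough to cut into the tolerance that the protocol itself allows.

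Second, no rule places a questionnaire completed between windows or before day 52. In a study without a strict schedule, where stopping nintedanib ends follow-up, some patients' last SGRQ may fall on such a day. The MMRM relies on data being missing at random given the observed scores. Dropping a score that was observed shortly before dropout removes information on which that assumption leans.

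**Working it through.** **Inputs.** Targets and limits come from the general window column of SAP Table 6.7:1. The ±1 month tolerance comes from Protocol section 9.2.3 and Table 2. Baseline is day 1. (The table's key puts questionnaires in Group 1, whose column as readable has entries only for baseline and FU1. That is a separate matter to check against the source table and is not used here.)

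**1. Rule behind the windows** (limit minus target).

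| Visit | Target | Window | Offsets | Length (days) |
|---|---|---|---|---|
| FU1 | 92 | 52-132 | -40/+40 | 81 |
| FU2 | 183 | 143-213 | -40/+30 | 71 |
| FU3 | 275 | 235-315 | -40/+40 | 81 |
| FU4 | 366 | 326-406 | -40/+40 | 81 |

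Target ±40 reproduces FU1, FU3 and FU4 exactly but gives 143-223 for FU2. Target ±30 gives 153-213. No symmetric half-width yields 143-213.

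**2. Unassigned days, 2 to 406.** Days 2-51 (50), 133-142 (10), 214-234 (21) and 316-325 (10): 50 + 10 + 21 + 10 = 91, of which 41 lie between visits. Days after 406 are also unassigned.

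**3. Windows against the protocol tolerance.** The ±1 calendar month limits were computed for every baseline date from 28 Feb 2019 to 28 Feb 2022 (1,097 dates).

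| Visit | Earliest allowed day | Latest allowed day, by baseline date | SAP window | Result |
|---|---|---|---|---|
| FU1 | 60 | 121-124 | 52-132 | inside, 8 days to spare |
| FU2 | 151 | 213-216 | 143-213 | up to 3 days outside |
| FU3 | 243 | 304-307 | 235-315 | inside, 8 days to spare |
| FU4 | 335 | 394-398 | 326-406 | inside, 8 days to spare |

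For FU2 the upper limit passes day 213 for 670 of the 1,097 baseline dates (61%). With a fixed month of 28 or 30 days, every in-tolerance visit is kept. With 31 days, day 214 is lost.

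**4. Does any rule rescue a gap-day record?** The duplicate rule chooses between two records inside one interval and does not bring in a record from outside. The broad post-baseline definition in section 7.4.1 admits the score in principle but gives it no visit, and the model needs one. SAP section 6.6 plans no imputation. A patient whose only follow-up SGRQ lies in a gap therefore contributes no post-baseline response.

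**5. Number of records: illustration only.** Protocol section 9.5 expects 17-20% dropout among 240, so 240 × 0.17 = 41 to 240 × 0.20 = 48 patients. The timing is not given. If every one left an SGRQ on a day spread uniformly over days 2-366, the count in gaps would be 41 × 91/365 ≈ 10 to 48 × 91/365 ≈ 12. If half stopped by day 92, it would be about 14-17. If discontinuations were recorded only at scheduled visits within tolerance, it would be near zero.

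**6. Effect of the fixes.** Extending FU2 to 223 lowers the unassigned total from 91 to 91 - 10 = 81 and covers day 216. Midpoints between targets are (92+183)/2 = 137.5, (183+275)/2 = 229 and (275+366)/2 = 320.5. Cutting there closes all three between-visit gaps.

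**The case against.** The strongest reply is that the windows are mostly wider than the protocol tolerance. At 3, 9 and 12 months no in-tolerance visit is lost, and at 6 months at most three days are. That stands. A reader might infer that routine visits are widely lost, or that 91 of 405 days means 22% of records. The documents support neither: those are calendar days, and 50 of them (days 2-51) hold no scheduled visit. Likewise, 61% is a share of baseline dates whose latest allowed day is out of window, not a share of visits.

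A reader might also infer that early discontinuers always lose their only follow-up score and that missing-at-random therefore fails. This is not established. The end-of-study visit is the one at which discontinuation is recorded, which may be the routine 3-month visit. Protocol Table 1 variables are documented if available. An early discontinuation questionnaire is possible, but its frequency and effect are unknown.

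Leaving very early records out of the 3-month mean is also defensible. SGRQ Part 1 asks about the past four weeks, so a record before about day 29 reaches back before baseline.

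Finally, the SAP never says that out-of-window records are excluded, parts of it are blacked out, section 6.6 breaks off mid-sentence, and the study is exploratory and descriptive. These points limit confidence in the consequence. They do not explain the FU2 limit or supply a rule for gap days.

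**Conclusion.** The point holds in a limited form. The FU2 upper limit breaks the SAP's own ±40 pattern and can exclude a protocol-compliant 6-month visit on days 214-216. Forty-one days between visits and 50 days before FU1 have no analysis visit, so an off-schedule or discontinuation SGRQ on those days has no place in the primary tables or model, although section 7.4.1 would count it as post-baseline.

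The window arithmetic is exact. Exclusion is inferred from three things: tables built on re-calculated visits, a by-visit model, and a duplicate rule that works only within an interval. The number of records affected, and any bias in the SGRQ change, cannot be computed from the documents; the counts in step 5 rest on assumed timing. It is a correction worth making because observed primary data are at stake and the repair is cheap, not because a large loss has been shown.

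**What to change.** Edit SAP Table 6.7:1 before database lock.

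- **Minimum:** set the FU2 upper limit to at least 223, and state what happens to a record outside every window.
- **Preferred:** make the windows contiguous at the midpoints: FU1 52-137, FU2 138-229, FU3 230-320, FU4 from 321 with its upper limit stated. Keep the closest-to-target rule for duplicates. Day 229 is equidistant from both targets; these limits place it in FU2.
- **Discontinuation visits from day 52 on:** assign the questionnaire to the nearest scheduled visit.
- **Before day 52:** keep these records out of the main 3-month estimate, or pre-specify their place, and include them in a sensitivity run.

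Report how many SGRQ records remain unassigned. No new data are needed. The small cost is that some records sit further from their nominal day: between visits, at most 46 days (229 - 183) instead of 40.
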